1.2. SCHEDULE OF EVENTS

Table 1 Schedule of Assessments

Study Period	Screening/ Baseline			Treatment			Post-Treatment Follow-up
	Visit Week 4	Visit 2 Week 1	TC 1 ^a	TC 2 ^a	Visit 3 Week 4 (EOT) or EW	Visit 4 Week 6 (EOS)	
	Study Week Visit Day (Window)	Day 1	Day 3 + 1	Day 7 +3	Day 25 +2	Day 28 +3	Day 42 +3
Informed Consent/Assent	X						
Inclusion/Exclusion Criteria	X	X					
Demography	X						
Medical History (including GI and bowel habits)	X	X					
Prior and Concomitant Medications	X	X	X	X	X	X	X
Physical Examination ^b	X	X			X		X
12-lead Electrocardiogram ^c	X						
Vital Signs ^d	X	X			X		X
Pregnancy Test (urine) ^e	X	X			X		X
Urine Drug Screen for Opioids ^f	X	X					
Serum Chemistry, Hematology, Urinalysis	X	X				X	
TSH (include T3 and T4 only if TSH is abnormal)	X						

Study Period		Screening/ Baseline		Treatment				Post-Treatment Follow-up	
Visit Study Week	Visit 1 Week 4	Visit 2 Week 1	TC 1 ^a	TC 2 ^a	TC 3 ^a	Visit 3 Week 4 (EOT) or EW	Visit 4 Week 6 (EOS)		
Visit Day (Window)	Day-28	Day 1	Day 3 + 1	Day 7 +3	Day 25 +2	Day 28 +3	Day 42 +3		
PK Sampling: Pre-dose on Day 1 on Day 28		X				X			
Intensive PK Sampling: Pre-dose and at 30, 60, 90, and 120 min post-dose in a subset of 70 subjects on Day 1		X							
Electronic Diary Training and Activation ^g		X							
Diary Eligibility ^h		X							
Randomization		X							
Study Drug Dispensation and Administration ⁱ		X							
In clinic PRO Assessments ^j		X				X	X		
Study Drug Collection and Accountability ^k		X				X	X		
Rescue Medication Dispensation		X	X ^l	X	X		X ^l		
Adverse Events ^m		X	X	X	X	X	X		

TC = Telephone Contact; EOT = end of treatment; EW = early withdrawal; EOS = end of study; GI = gastrointestinal; PK = pharmacokinetic; PRO = Patient reported outcome; TSH = thyroid-stimulating hormone.

- In addition to on-site clinic visits, study sites will call subjects/caregivers on Day 3, Day 7, and as needed to remind them to complete their daily diaries and on Day 25 to remind them to return all unused study drug at their EOT visit.

- b. Physical examination (PE), including body weight measurement, will be performed at Visit 1. A symptom-directed PE will be performed as necessary at Visit 3 (EOT) or EW and Visit 4 (EOS); height is measured at the Screening Visit. Body mass index (BMI) will be calculated by Electronic Data Capture (EDC) at the Screening Visit only. Height and body weight may be collected at Visit 2 if missed at Screening.
- c. The standard 12-lead Electrocardiogram (ECG) will be performed in the semi-recumbent or supine position.
- d. Seated blood pressure, heart rate, respiration, temperature.
- e. Urine pregnancy tests on-site at clinic visits for female subjects as per exclusion criteria 5
- f. Urine drug screen for selected opioids (screen includes methadone, morphine and oxycodone) will be performed on-site; a negative result must be confirmed prior to dispensing the study medication.
- g. Clinical site personnel will train subjects on the use of electronic diaries at the Screening visit and remind them to make daily entries throughout the study, with retraining as needed. The interactive voice or web response system will provide daily reminders to improve compliance, and as per bullet a, study sites will call subjects/caregivers on day 3, day 7, and weekly until Visit 3 (Week 4) to remind them to complete their daily diaries.
- h. Baseline diary results will be reviewed programmatically and a "Diary Eligible" or "Not Diary Eligible" report will be provided to the site immediately prior to randomization.
- i. Subjects will take their first dose of study drug at the site on Day 1; it is recommended that for dosing at home, subjects take it once daily at approximately the same time in the morning.
- j. Details on timing of each PRO Assessment will be included in the Study Procedure Manual.
- k. Study drug not returned at EOT must be returned at EOS
- l. Only if needed
- m. Adverse Event collection begins immediately after informed consent is signed. A symptom-directed physical examination should be performed as appropriate at discretion of the investigator.

1.3. GLOSSARY OF ABBREVIATIONS

AE	Adverse Event
ANCOVA	Analysis of Covariance
ANOVA	Analysis of Variance
ATC	Anatomical Therapeutic Chemical
BLQ	Below the Limit of Quantification
BM	Bowel Movement
BMI	Body Mass Index
BSFS	Bristol Stool Form Scale
CI	Confidence Interval
CMH	Cochran-Mantel-Haenszel (Test)
CRF	Case Report Form
CSBM	Complete Spontaneous Bowel Movement
CTCAE	Common Terminology Criteria for Adverse Events
ECG	Electrocardiogram
eCRF	Electronic Case Report Form
EDC	Electronic Data Capture
EOS	End of Study
EOT	End of Treatment
FAS	Full Analysis Set (Population)
FDA	Food and Drug Administration
GI	Gastrointestinal
IBS	Irritable Bowel Syndrome
IBS-C	Irritable Bowel Syndrome with Constipation
IWRS	Interactive Web-Based Response System
LLOQ	Lower Limit of Quantification
LS	Least Squares
mBSFS-C	Modified Bristol Stool Form Scale for Children
MedDRA	Medical Dictionary for Regulatory Activities
MG	Milligram
PE	Physical Examination
PK	Pharmacokinetic
PP	Per-Protocol (Population)
PRO	Patient Recorded Outcome
RM	Rescue Medication
SAE	Serious Adverse Event
SBM	Spontaneous Bowel Movement
SD	Standard Deviation
SOC	System Organ Class
TC	Telephone Contact
TEAE	Treatment Emergent Adverse Event
TSH	Thyroid Stimulating Hormone
ULN	Upper Limit of Normal

2. OBJECTIVES

Primary Objective:

To evaluate the safety and efficacy of once daily oral plecanatide for 4 weeks as treatment for the relief of symptoms associated with Irritable Bowel Syndrome with Constipation (IBS-C) in children ages 6 to < 18 years.

Secondary Objective:

To estimate the pharmacokinetic (PK) parameters of plecanatide in this subject population (to the extent possible, since plecanatide is not expected to be absorbed).

3. GENERAL STATISTICAL CONSIDERATIONS

3.1. SAMPLE SIZE AND POWER

Based on data from two phase 3 trials conducted by the sponsor in adults with IBS-C, consider the sample size necessary for observing a significant difference in the change from baseline in SBM frequency in Group B (the adolescents) since data from the adults is likely more applicable to Group B participants. Then, a study with a plecanatide group sample size of 102 and a placebo group sample size of 34 (representing 3:1 randomization, plecanatide to placebo) achieves 81.5% power at the 0.05% level of significance when the difference in mean change from baseline in weekly SBM frequency at four weeks is 1.5 and the placebo group and plecanatide group standard deviations are 2.3 and 3.5 respectively. Since study SP304202-14 is being conducted in children and adolescents with IBS-C, and the primary analysis of the primary endpoint will be an ANCOVA using a linear mixed-effects model, the sponsor believes that 30 subjects per treatment group (placebo and 3 dose levels of plecanatide), yielding a planned target enrollment of a total of 210 subjects (90 children and 120 adolescents), will prove sufficient for achieving the primary objective of this phase 2 study.

3.2. RANDOMIZATION AND MASKING

This is a double-blind, placebo-controlled study with seven treatment age/dose groups that will be conducted at up to approximately 20 clinical sites. Subjects 6-11 years of age will be randomly assigned to 1 of 3 treatment groups (2 active treatments, 1 matching placebo) in a 1:1:1 ratio stratified by gender and subjects 12 to < 18 years of age will be randomly assigned to 1 of 4 treatment groups (3 active treatments, 1 matching placebo) in a 1:1:1:1 ratio stratified by gender using an Interactive Web-based Response System (IWRS).

Central, block randomization will be performed with stratification by gender.

Age Dose Group		Treatment		No. of Tablets to be Taken Daily	Dose Level	Number of Subjects
A	6 to 11 yrs. old	1	0.5 mg plecanatide	1	0.5 mg plecanatide	30
A	6 to 11 yrs. old	2	1.0 mg plecanatide	1	1.0 mg plecanatide	30

A	6 to 11 yrs. old	3	Matching placebo	1	placebo	30
B	12 to < 18 yrs. old	4	0.5 mg plecanatide	2	1.0 mg plecanatide	30
B	12 to < 18 yrs. old	5	1.0 mg plecanatide	2	2.0 mg plecanatide	30
B	12 to < 18 yrs. old	6	1.5 mg plecanatide	2	3.0 mg plecanatide	30
B	12 to < 18 yrs. old	7	Matching placebo	2	placebo	30

The study will be performed in a double-blind manner. All study drugs will be supplied in identical blister packs and tablets will be similar in color, smell, taste, and appearance, thereby assuring double-blind conditions.

The gender-stratified randomization schedule was prepared by Foehl Statistics & Analytics LLC.

3.3. HANDLING OF DATA

3.3.1. Strata and Covariates

Enrollment will be stratified by age group (6 to 11 years and 12 to < 18 years). Randomization will be stratified by gender to ensure gender balance across treatment groups.

3.3.2. Examination of Subject Subsets

No further examination of subject subsets will be performed.

3.3.3. Multiple Testing and Comparisons

Since this is a Phase 2 clinical trial for exploratory purposes, no adjustments for multiple comparisons will be undertaken.

3.3.4. Missing Data

Missing values of safety parameters will not be imputed.

For each day in the week for which the Bowel Movement (BM) (includes Spontaneous Bowel Movement [SBM] and Complete Spontaneous Bowel Movement [CSBM]) response is missing, 0 BMs (SBMs, CSBMs) will be used, and any week in which no BM response is recorded, the weekly BM (SBM, CSBM) rate will be set to 0. In particular, for a randomized subject who withdraws from study participation prior to the end of the study, the subject is considered to have a weekly BM (SBM, CSBM) rate equal to 0 for any weeks remaining in the planned duration of the study for which the subject has no BM responses recorded.

In any analysis of the frequency of abdominal pain (discomfort), use of rescue medication, the frequency of fecal incontinence, the frequency of defecation pain, the frequency of large diameter stools, missing values will be imputed to zero.

In any analysis involving the severity of abdominal pain and discomfort, the weekly average IBS-related daily abdominal pain (discomfort) score is the average of the non-missing, abdominal pain (discomfort) scores recorded in that week, i.e., the weekly average is the sum of the abdominal pain (discomfort)

scores recorded in the diary in the given week, divided by the number of pain (discomfort) scores recorded in the week. In any week in which a subject has no diary days for which an abdominal pain (discomfort) score is recorded, the weekly average abdominal pain (discomfort) score will be set to missing. In particular, for a randomized subject who withdraws from study participation prior to the end of the study, the weekly average abdominal pain (discomfort) score will be set to missing for any weeks remaining in the planned duration of the study for which the subject has no abdominal pain (discomfort) data.

In any analysis involving the severity of defecation pain, the weekly averages are the sum of the non-missing severity of defecation pain scores recorded during the week, divided by the total number of non-missing severity of defecation pain scores recorded. In any week in which a subject has no non-missing severity of defecation pain scores recorded, the weekly average score will be set to missing in any summary or linear mixed-effects model analysis involving the weekly average severity of defecation pain score.

In any analysis involving stool consistency (mBSFS-C scores or BSFS scores), the determination of weekly averages will follow the same methodology as presented above for abdominal pain. However, since stool consistency cannot be assessed if the subject does not have at least one SBM during the week in question (i.e., stool consistency is based on SBMs only), the weekly average will also be set to missing if no SBMs are recorded for any days in the week. Also, it is possible that a subject has no baseline weekly average stool consistency score because of the SBM criterion; in that case the subject will be excluded from any change from baseline analyses of stool consistency.

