5.2.8 Early Withdrawal/Early Termination Visit (EW/ET)

Patients are free to withdraw from participation in the study at any time. Investigators may choose to discontinue a patient's participation in the study if they believe it is in the patient's best interest clinically. If a patient's post-randomization compliance is of concern, contact the medical monitor to discuss. If the patient has an intervening illness that requires discontinuation of study participation, the patient and Investigator will follow procedures for early withdrawal. The following are examples of AEs that qualify for Early Withdrawal (EW):

- A positive pregnancy test will require discontinuation from the study (see **Section 7.7**).
- Changes in laboratory values, PE findings, or other assessments considered by the Investigator (or designee) to be clinically significant will require discontinuation from the study.
- Clinically significant TEAEs, including clinically significant laboratory test abnormalities or SAEs regardless of relatedness to study treatment that cause the patient, investigator, or Sponsor to feel it is not in the patient's best interest to continue.

A patient may also be withdrawn from study drug/study by the Sponsor, regulatory authorities, or the institutional review board (IRB). Patients will also be withdrawn if the entire study is terminated prematurely as described in **Section 9.9**.

Patients who discontinue early from the study should, if possible, have an Early Withdrawal Visit. The Investigator must make every effort (with proper documentation) to have the patient complete this final visit. This visit should take place as soon as possible (and within 5 days) after the patient stops taking study drug.

The following procedures will be performed at the Early Withdrawal Visit:

- Collect/record unused study drug from the supply dispensed at the previous visit
- Have the patient/caregiver complete the PRO questionnaires (see Study Procedure Manual)
- Assess/record changes in concomitant medications and diet
- Symptoms directed physical examination and vital signs (seated blood pressure, heart rate, respiration, and body temperature)
- Safety laboratory assessments (hematology, serum chemistry, urinalysis)
- Perform urine pregnancy test, if applicable
- Collect blood samples for plecanatide/SP-338 assessments
- Assess adverse events.

In all cases, a single, primary reason for withdrawal must be recorded on the eCRF.

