8.4.1 Missing Data Conventions

Missing values of safety parameters will not be imputed.

The weekly BM (SBM, CSBM) rate is the sum of the BMs (SBMs, CSBMs) recorded for the days in the week for which a BM response is recorded in the daily diary. Note that this is equivalent to a “worst case” analysis in that the BM (SBM, CSBM) rate for the week is the sum of the BMs (SBMs, CSBMs) recorded for the days in the week for which BMs were reported, plus 0 BMs (SBMs, CSBMs) for each day in the week for which the BM response is missing. In any week in which no BM response is recorded, the weekly BM (SBM, CSBM) rate will be set to 0 in any summary or linear mixed-effects model analysis involving

the weekly BM (SBM, CSBM) rate. In particular, for a randomized patient who withdraws from study participation prior to the end of the study, the patient is considered to have a weekly BM (SBM, CSBM) rate equal to 0 for any weeks remaining in the planned duration of the study for which the patient has no BM responses recorded.

The weekly average IBS-related daily abdominal pain score is the average of the non-missing, abdominal pain scores recorded in that week, i.e., the weekly average is the sum of the abdominal pain scores recorded in the diary in the given week, divided by the number of pain scores recorded in the week. In any week in which a patient has no diary days for which an abdominal pain score is recorded, the weekly average abdominal pain score will be set to missing. In any linear mixed-effects model analysis involving the weekly average abdominal pain score, if the average score is set to missing in a given week, it will be left as missing in the linear model. In particular, for a randomized patient who withdraws from study participation prior to the end of the study, the weekly average abdominal pain score will be set to missing for any weeks remaining in the planned duration of the study for which the patient has no abdominal pain data.

In any analysis of the frequency of fecal incontinence, the frequency of defecation pain, and the frequency of large diameter stools will follow the same methodology as described above for the determination and analysis of the weekly BM rate.

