4.2. PER PROTOCOL (PP) POPULATION

All subjects in the FAS population who complete the 4-week Treatment Period or discontinue from study treatment due to adverse event(s) or lack of efficacy, with the exception of major protocol violators. If a diary compliance is < 70% or treatment compliance is < 80% then the subject is excluded from the PP Population. Subjects with Week 4 visit outside of the window 28 +/- 3 (study days 25 to 31) days will be excluded from the PP Population. Final decisions regarding exclusion from the PP Population will be made prior to unblinding the database.

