5.2. EFFICACY ANALYSIS

5.2.1. Primary Efficacy Endpoint

The primary efficacy endpoint is the change from baseline in weekly SBM frequency over the 4 Week Treatment Period compared to placebo across treatment groups.

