5.2.2. Primary Efficacy Analysis

The weekly SBM rate for each subject will be computed for each week of the 4-week treatment period. The change from baseline in mean weekly SBM rate will be analyzed using a linear mixed-effects model with fixed effects for gender (stratification variable), treatment, week, the interaction of treatment and week, and the corresponding baseline value; a random intercept for subject will also be specified. The least squares (LS) mean change from baseline will be presented, by treatment groups, and the difference in LS means for each treatment group versus placebo and combined active doses within each age group versus placebo in a separate model for each age group, and overall active doses versus placebo in a separate model with 95% confidence intervals and corresponding statistical p-values.

The baseline SBM weekly rate will be the weekly average number of SBMs recorded during each of the 2 weeks preceding initiation of study drug.

The above analysis will be repeated for the PP Population.

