7. CHANGES IN THE PLANNED ANALYSES

In accordance with the FDA guidance (FDA Guidance on Conduct of Clinical Trials of Medical Products during COVID-19 Pandemic, March 2020), processes were put in place to ensure that any impacted study assessments can be identified in the study database. Any impacted assessments for subjects participating in this study will be identified in the relevant individual subject listings. Any subject discontinued due to COVID-19 disruption, will be noted as such in the subject disposition summary and associated individual subject listing.

SAP Version 2.0 changes: For the Per Protocol population, the compliance threshold for eDiary was updated to eDiary compliance of at least 70% instead of at least 80%. Overall, this eDiary compliance threshold is considered adequate in this pediatric subject population and in the context of the COVID-19 pandemic.

The Per Protocol population was also updated to expand visit windowing for Visit 3/Week 4 from the protocol-specified window of 28 +3 days. to 28 days plus or minus 3 days. Protocol-specified visit window is 28 to 31 days, however it is expected that a subject with Week 4 completed in the 25 to 31 day window, with adequate treatment compliance and diary compliance as specified for the PP Population, is reflective of 4 weeks of study treatment, as intended by the study objectives.

Clarification was added for the pharmacokinetic analyses, utilizing actual sampling times for PK parameter estimation, and also to state the definitions for Cmax, Tmax, and Cmin.

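### The primary analysis scores post-withdrawal weeks as zero bowel movements even when the withdrawal is due to COVID-19 disruption or study termination

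*Combined protocol and SAP*

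**What the plan says.** The primary endpoint (SAP 5.2.1) is the "change from baseline in weekly SBM frequency over the 4 Week Treatment Period compared to placebo across treatment groups". SAP 5.2.2 analyses the weekly rates in a linear mixed model with gender, "treatment, week, the interaction of treatment and week, and the corresponding baseline value; a random intercept for subject will also be specified". The FAS is the main efficacy population (SAP 4.1). It keeps withdrawn children who have a baseline and at least one post-randomization SBM assessment.

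SAP 3.3.4 says that a subject who withdraws early "is considered to have a weekly BM (SBM, CSBM) rate equal to 0 for any weeks remaining in the planned duration of the study", limited to weeks without any recorded bowel-movement response. Single days without a response also count as 0. Protocol 8.4.1 has the same rule and describes it as a worst-case analysis: in a week with no response, "the weekly BM (SBM, CSBM) rate will be set to 0 in any summary or linear mixed-effects model analysis involving" that rate.

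The documents foresee external loss in two places. SAP section 7 states: "Any subject discontinued due to COVID-19 disruption, will be noted as such in the subject disposition summary", and adds a subject listing. Protocol 5.2.8 states: "Patients will also be withdrawn if the entire study is terminated prematurely"; protocol 9.9 allows termination for slow enrollment or a sponsor decision. Neither place changes how the primary variable is derived.

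The per-protocol (PP) population (SAP 4.2) starts from FAS subjects "who complete the 4-week Treatment Period or discontinue from study treatment due to adverse event(s) or lack of efficacy". For abdominal pain severity, SAP 3.3.4 leaves post-withdrawal weeks missing.

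**The concern.** A weekly rate of 0 is not a no-change value. It makes the change from baseline equal to minus the baseline, which is worse than no response. That can be defended as a penalty when a child stops for lack of efficacy or intolerance. It says nothing about the drug when the child stops because of a pandemic restriction or because the sponsor ends the trial.

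Take a child with a baseline of 3 SBMs per week and 6 per week in Weeks 1 and 2, who is then withdrawn for an external reason. The weekly changes are +3, +3, -3 and -3, a four-week mean of 0. The observed weeks alone give +3.

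The primary estimate would then combine the effect of plecanatide with the chance of being hit by outside events. No planned analysis keeps these children's observed weeks and treats the lost ones as missing.

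**Working it through.** **Inputs from the documents.** Difference 1.5 SBMs per week; SDs 3.5 (plecanatide) and 2.3 (placebo); 102 versus 34 in the power statement (SAP 3.1, protocol 8.2). Planned Group B size is 90 active versus 30 placebo. Alpha is 0.05 two-sided (SAP 5).

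**Assumptions, because the documents give no withdrawal rate.** A share q of each arm is withdrawn for external reasons and loses a fraction f of the four treatment weeks, independently of outcome. Placebo mean change 1.0, baseline mean 2 to 3 SBMs per week, baseline SD 1.2.

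**1. The plan's own figure.** Normal approximation: power = Φ(difference/SE − 1.96).
- 102 versus 34: SE = √(3.5²/102 + 2.3²/34) = 0.525; 1.5/0.525 = 2.857; power 81.5%. This reproduces the stated value at two-sided 5%. The printed 0.05% level would give 26.6%, so 5% was evidently meant.
- 90 versus 30: SE = 0.559; 1.5/0.559 = 2.684; power 76.5%. This is the no-loss reference.

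**2. Expected difference under the zero rule, balanced loss.** With true mean change μ and baseline b, an arm's expected change is (1 − qf)μ − qf·b. The baseline term cancels between arms, so the difference is 1.5 × (1 − qf). The relative loss is qf, the share of patient-weeks lost.

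**3. Size with f = 0.5.** The SDs are recalculated for the mixture of affected and unaffected children.

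| q | Expected difference | Power, baseline 2 | Power, baseline 3 |
|---|---|---|---|
| 0 | 1.50 | 76.5% | 76.5% |
| 5% | 1.5 × 0.975 = 1.46 | 75.1% | 74.5% |
| 10% | 1.5 × 0.95 = 1.43 | 73.6% | 72.5% |
| 20% | 1.5 × 0.90 = 1.35 | 70.8% | 68.8% |

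**4. Check in a mixed model.** Simulation with a random intercept, 90 versus 30, baseline mean 2, one to three weeks observed per affected child, 150 runs per scenario, simulation SE 0.04. The zero rule gave 1.46 (q = 10%) and 1.33 (q = 20%). Leaving the lost weeks missing gave 1.54 and 1.47, both consistent with 1.5.

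**5. Imbalance.** With f = 0.5 and baseline 2:
- 15% of active and 10% of placebo children affected: 2.1625 − 0.85 = 1.31.
- 5% of active and 15% of placebo children affected: 2.3875 − 0.775 = 1.61, away from zero.

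In one arm of 30, a child with an on-treatment rate of 4.5 per week who loses k of 4 weeks lowers the arm mean by 4.5 × (k/4)/30: 0.04 for one week, 0.075 for two, 0.11 for three.

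**The case against.** **The rule is deliberate.** It is disclosed as worst case in protocol 8.4.1, and the opening of protocol section 8 says the SAP will leave the primary analysis unchanged. This stands. It means that an edit to the SAP alone would contradict the protocol. It does not make zero a sensible value for a loss unrelated to treatment.

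**Disruption may cost few treatment weeks.** SBM data come from a home electronic diary, four weeks of drug are dispensed on Day 1, and the protocol's visit procedures list only telephone contacts between Day 1 and Day 28. A missed Visit 3 or 4 need not remove any diary week, and Weeks 5 and 6 are outside the primary endpoint. This also stands, and favours the lower part of the range.

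**The PP repeat helps.** A reader might infer that nothing planned reveals or removes the dilution. That is too strong. The PP set omits these children, which removes the dilution if loss is unrelated to outcome. It costs their observed weeks, and because it also excludes for diary compliance, treatment compliance and Week 4 timing, a gap between FAS and PP results cannot be attributed to this rule.

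**The direction is not fixed.** A reader might also infer that the rule always pulls the effect toward zero. It does so only in expectation, with balanced loss and a positive true effect; 1.61 above is the counter-example.

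**Conclusion.** The concern holds as a flaw in how the primary variable is defined: externally caused weeks without diary data receive the worst possible value, whatever the reason for withdrawal. With balanced loss the attenuation equals the share of treatment patient-weeks lost: 2.5%, 5% or 10% if 5%, 10% or 20% of children lose half their weeks. These rates are assumptions, and the true size cannot be derived from the documents. For a single dose contrast, each affected child can matter by about 0.04 to 0.11 SBM per week, in either direction.

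The problem is mainly one of bias. A reader might infer that leaving the weeks missing would restore planned power, but lost data stay lost: dropping these children altogether gives 72.1% at q = 10% and 67.0% at q = 20%. Nor do the documents support treating severe imbalance as likely. If 5% are affected and the weeks lost are evenly one, two or three, two arms of 30 differ by two or more children losing three weeks about 12% of the time.

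The change is worth making, but the trial does not depend on it: the study is exploratory and the likely effect is modest.

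**What to change.** Before unblinding, restrict the zero rule by recorded reason. Use a closed list, COVID-19 disruption and study termination, confirmed for each child at the blinded data review. For these children, set weeks without diary data, and days after the withdrawal date, to missing, and keep their observed weeks in the mixed model. State how a rate is formed from the part-observed withdrawal week. An open category of other unrelated reasons should be avoided, because it would need case-by-case judgement.

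There are two consistent ways to adopt this:
- amend protocol 8.4.1 together with SAP 3.3.4 and SAP section 7; or
- keep the worst-case rule as primary and add this as a prespecified FAS sensitivity analysis, reported beside it. This avoids changing the primary analysis.

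The cost is small. The eCRF already records one primary reason for withdrawal (protocol 5.2.8), COVID-19 discontinuations are already identified (SAP section 7), and a blinded data review meeting is already planned (SAP 3.4). What is added is one derivation flag, a short blinded classification step, a missing-at-random assumption for the affected weeks and, under the first option, a protocol amendment.
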